8. OTHER STATISTICAL ANALYSES

8.1. Efficacy Analyses

8.1.1. Principal Secondary Efficacy Analyses

8.1.1.1. Overview of Planned Principal Secondary Efficacy Analyses

Table 6 provides an overview of the planned principal secondary efficacy analyses.

Table 6 Overview of Planned Principal Secondary Efficacy Analyses

	Analysis	Absolute								
Endpoint	Analysis	Sta	ts Analy	/sis	Sum	mary	Individual			
-	Population	Т	F	L	Т	F	F	L		
Iron Use										
Average monthly IV iron dose (mg)/subject to Week 52	ITT	Y			Y	Y		Y		
Supportive analysis: Average monthly IV iron dose (mg)/subject to Week 52 using on and off- treatment IV iron records	ITT	Y			Y	Y				
By subgroup	ITT	Y	Y							

NOTES:

- T = Table, F = Figure, L = Listing, Y = Yes display generated.
- Stats Analysis = Represents TFL related to any formal statistical analyses (i.e. modelling) conducted.
- Summary = Represents TFL related to any summaries (i.e. descriptive statistics) of the observed raw data.
- Individual = Represents FL related to any displays of individual subject observed raw data.

8.1.1.2. Planned Principal Secondary Efficacy Statistical Analyses

Principal Secondary Efficacy Statistical Analyses: Average Monthly IV Iron Dose
Endpoint(s)

• Average monthly IV iron dose (mg)/subject to Week 52

Model Specification

- Average monthly IV iron dose (mg)/subject from baseline to Week 52 will be determined by calculating the total IV iron dose per subject from treatment start date + 1 to the earliest of (Week 52 visit date, first blood (RBC or whole blood) transfusion date, and treatment stop date + 1 day) which corresponds to the time while the subject was on randomized treatment and before receiving a blood transfusion. This total IV iron dose will be divided by (the number of days from treatment start date + 1 to the earliest of (Week 52 visit date, first blood transfusion date (RBC or whole blood), and treatment stop date +1) /30.4375 days). See Section 10.4.1 for the definition of on-treatment IV iron.
- An ANCOVA model will be used to compare the difference in average monthly IV iron dose per subject between arms, adjusting for:
 - o Treatment
 - Baseline monthly IV iron dose (see Section 10.5.2)
 - Dialysis type (as randomized, see Section 10.10.2)
 - Region (as randomized, see Section 10.9 & Section 10.10.2)

200807

20001
Principal Secondary Efficacy Statistical Analyses: Average Monthly IV Iron Dose
Model Results Presentation
 The number and percentage of subjects with baseline IV iron use, on-treatment EP IV iron use, and on-treatment IV iron use to Week 52 will be summarized by treatment. Average monthly IV iron dose at baseline, while on treatment during the EP, and while on
treatment to Week 52 will be summarized by treatment group using mean, standard deviation, minimum, P25, median, P75, and maximum.
 The least square (LS) mean estimates and standard errors by treatment group, LS mean difference, two-sided 95% CI and one-sided superiority p-value for the difference in average monthly IV iron dose/subject to Week 52 between the daprodustat and rhEPO arms from the ANCOVA model will be presented. The number of subjects contributing to the analysis and the associated mean and standard deviation of the baseline and Week 52 values will also be displayed with the results of the ANCOVA model.
• A listing of average monthly IV iron dose will be provided including treatment, site ID, unique subject ID, time period, and average monthly IV iron dose at Week 52.
Model Results Interpretation
See Section 10.11.1.
Supportive Statistical Analyses
Average monthly IV iron dose (mg)/subject to Week 52 using on and off treatment IV iron
records, regardless of transfusion
 The summaries and analysis described above for the principal secondary average monthly IV iron dose/subject to Week 52 will be repeated using all available IV iron records during the Day 1 – Week 52 visits, regardless of whether or not a subject was on treatment or transfusion.
• The average monthly IV iron dose (mg)/subject to Week 52 for this analysis will be determined by calculating the total IV iron dose per subject from Day 1 to the earliest of Week 52 visit date,

 The average monthly iv from dose (mg)/subject to week 52 for this analysis will be determined by calculating the total IV iron dose per subject from Day 1 to the earliest of Week 52 visit date, study completion/withdrawal date) and dividing by (earliest of the (Week 52 visit date, study completion/withdrawal date) – Randomization date + 1 day/30.4375 days).

Subgroup Analysis

• Subgroup analysis details are discussed in Section 10.10.1.

8.1.2. Additional Secondary Efficacy Analyses

8.1.2.1. Overview of Planned Additional Secondary Efficacy Analyses

Table 7 provides an overview of the planned additional secondary efficacy analyses.

200807

Endpoint	Analysis		Absolute				Change from Baseline								
	Popula-	Stats			Sum	mary	Individual		Stats		S		mary		ridual
	tion		nalys	IS	-		_	-		naly	SIS	–		_	
		Т	F	L	Т	F	F	L	Т	F	L	T	F	F	L
Hgb Variability			1	1	1	1	1	1	1	1	1	1	1	1	1
Hgb change from baseline to Week 52 ^{1, 2}	ITT								Y	Y		Y			
Hgb change from baseline to Week 52 by subgroup ^{1,2,3}	ITT								Y	Y					
Hgb respon- ders ²	ITT	Y			Y										
Hgb responders by subgroup ^{2,3}	ITT	Y	Y												
% of time Hgb in analysis range ²	ITT	Y			Y										
% of time Hgb in analysis range by subgroup ^{2,3}	ITT	Y	Y												
Time to Rescue								1							
Time to stopping randomized treatment due to meeting rescue criteria	ITT	Y	Y		Y										
Time to stopping randomized treatment due to meeting rescue criteria by hyporesponder subgroup	ITT	Y													

Table 7 Overview of Planned Additional Secondary Efficacy Analyses

NOTES:

• T = Table, F = Figure, L = Listing, Y = Yes display generated.

• Stats Analysis = Represents TFL related to any formal statistical analyses (i.e. modelling) conducted.

• Summary = Represents TFL related to any summaries (i.e. descriptive statistics) of the observed raw data.

• Individual = Represents FL related to any displays of individual subject observed raw data.

^[1] Analysis will be performed using all available (on and off-treatment) Hgb values.

^[2] Analysis will be performed using evaluable Hgb values only (see Section 10.6.3).

^[3] Subgroup analysis will only use the region and hyporesponder subgroups defined in Section 10.10.1.

200807

8.1.2.2. Planned Secondary Efficacy Statistical Analyses

Hgb Variability

Secondary Efficacy Statistical Analyses: Hgb Variability
Endpoint(s)
Hgb change from baseline to Week 52
• N (%) responders, defined as mean Hgb within the Hgb analysis range 10-11.5 g/dL during EP
• % time Hgb in analysis range (10-11.5 g/dL) during the evaluation period (EP, Week 28 to 52)
and during the maintenance period (MP; Week 28 to end of trial) (non-inferiority analysis that
will use a margin of 15 percentage points less time in range)
Model Specification
• For the secondary analysis of Hob change from baseline to Week 52, a mixed model repeated

- For the secondary analysis of Hgb change from baseline to Week 52, a mixed model repeated measures (MMRM) approach will be used with an unstructured covariance matrix to compare the difference in means between arms. The model will be fitted to Hgb data collected after baseline up to Week 52, excluding values collected during the stabilization period (Randomization date + 1 day to <Week 28). The model will include factors for treatment, time, prognostic randomization stratification factors (as randomized, see Section 10.10.2), baseline Hgb and the baseline Hgb by time and treatment by time interaction terms. Analyses will be done with the MIXED procedure in SAS, using the Kenward-Roger option to estimate denominator degrees of freedom and standard errors. This analysis will be performed using all available Hgb values (on and off-treatment) and separately using evaluable Hgb values only (see Section 10.6.3). In the analysis using all available Hgb values, subjects who withdraw from the study before Week 52 are considered to be missing at random and in the analysis using evaluable Hgb values, subjects who permanently discontinue randomized treatment before Week 52 are assumed to be missing at random.

- For the Hgb responder analysis, mean Hgb during the EP will be defined as in the while ontreatment supportive analysis (Section 10.6.3). Responders will be subjects with a mean Hgb during the EP that falls within the Hgb analysis range of 10-11.5 g/dL. A Cochran-Mantel-Haenszel (CMH) chi-squared test, adjusting for treatment and the prognostic randomization stratification factors (as randomized, see Section 10.10.2), will be used to compare the number and % of responders between the treatment groups.
- For the analysis of % time in range, the method by Rosendaal [Rosendall, 1993] will be used to calculate the percentage of time (days) a subject's Hgb is below, within and above the Hgb analysis range of 10 to 11.5 g/dL during the EP (Weeks 28-52) and separately during the MP (Week 28 end of study) (See Section 10.6.3). A van Elteren test (stratified Wilcoxon rank sum test) will be used to compare the percentage of time in range between treatment arms, adjusting for treatment and the prognostic randomization stratification factors (see Section 10.10.2). This analysis will be performed using evaluable Hgb values only. Hodges-Lehmann estimate of the treatment difference will be used to assess non-inferiority in % time in range.

Model Results Presentation

- For the MMRM analysis of change from baseline in Hgb, an LSMEANS statement will provide adjusted treatment group means and standard errors and a point estimate and two-sided 95% confidence interval for the adjusted mean treatment difference (daprodustat - rhEPO) at Week 52. The one-sided non-inferiority p-value for this test will be calculated.
- For the responder analysis, the number and percentage of subjects with mean EP Hgb, mean MP Hgb, and end of treatment Hgb above, within and below the Hgb analysis range will be

200807

summarized by treatment group.

- For the responder analysis, the number and % of responders by treatment group, difference in response rate (daprodustat vs rhEPO) and two-sided 95% CI using Wald method will be provided along with the one-sided CMH p-value for the treatment group comparison. If the CMH adjusted treatment difference is positive, then the one-sided p-value is p/2, and if the adjusted treatment difference is negative, then the one-sided p-value is 1-p/2, where p is the two-sided p-value from the CMH test.
- The % time Hgb is above, in and below the Hgb analysis range (10-11.5 g/dL) during the MP and the EP will be summarized using mean, standard deviation, minimum, P25, median, P75, and maximum by treatment group.
- The percent time in range for each treatment group, the stratified Mann-Whitey estimate of the treatment difference (daprodustat rhEPO) and associated two-sided 95% CI [Kawaguchi, 2011] will be presented in addition to the one-sided superiority p-value from the van Elteren test. Hodges-Lehmann estimate of the treatment difference (daprodustat-rhEPO) and associated two-sided 95% CI will be presented.

Model Results Interpretation

- For the MMRM analysis of change from baseline in Hgb, the NI margin used in the co-primary analysis of Hgb (-0.75 g/dL) will be used for reference in this comparison, thus generating support for non-inferiority if the lower bound of the two-sided 95% CI is above -0.75 g/dL.
- For the responder analysis, the one-sided CMH p-value will be compared to 0.025 to assess nominal significance.
- For the percent time in range analysis, a NI margin of -15% will be used as a reference in this comparison, thus generating support for non-inferiority if the lower limit of the two-sided 95% CI of Hodges-Lehmann estimate is above -0.15. If non-inferiority is established, nominal superiority will be achieved if the the one-sided p-value is < 0.025.

Supportive Statistical Analyses

Subgroup Analysis

• Subgroup analyses will be performed for all Hgb variability endpoints, using the region and hyporesponder subgroups only (described in Section 10.9.1 & Section 10.10), in a method similar to that described for the subgroup analyses of the co-primary and principal secondary analyses.

Time to Rescue

Secondary Efficacy Statistical Analyses	: Time to Rescue
Endpoint(s)	
• Time to stopping randomized treatment	due to meeting rescue criteria
Model Specification	
 Analysis of the endpoint above will be described for the co-primary MACE an 	performed using an analysis model identical to that alysis.
	endpoints occurring within the time period for treatment event or censoring is described in further detail in
Time to stopping study medication due	to meeting rescue criteria is defined as the time from

 Time to stopping study medication due to meeting rescue criteria is defined as the time from Randomization until the date on which a subject permanently stops study medication due to

200807

 meeting criteria for rescue. Model Results Presentation Summaries will include (see Section 10.6.3): the number and percentage of subjects meeting evaluation criteria for rescue and the number of occurrences (events), the number and percentage of subjects unable to be evaluated for rescue, and the number and percentage of subjects meeting rescue. The analysis model results presentation will be identical to the co-primary MACE model results, with the following exceptions: The one-sided p-value presented will be for the test of superiority of daprodustat vs. rhEPO. The forest plot figure will not be created for the time to stopping study medication due to meeting rescue criteria endpoint. Model Results Interpretation 	Secondary Efficacy Statistical Analyses: Time to Rescue
 Summaries will include (see Section 10.6.3): the number and percentage of subjects meeting evaluation criteria for rescue and the number of occurrences (events), the number and percentage of subjects unable to be evaluated for rescue, and the number and percentage of subjects meeting rescue. The analysis model results presentation will be identical to the co-primary MACE model results, with the following exceptions: The one-sided p-value presented will be for the test of superiority of daprodustat vs. rhEPO. The forest plot figure will not be created for the time to stopping study medication due to meeting rescue criteria endpoint. 	meeting criteria for rescue.
 the number and percentage of subjects meeting evaluation criteria for rescue and the number of occurrences (events), the number and percentage of subjects unable to be evaluated for rescue, and the number and percentage of subjects meeting rescue. The analysis model results presentation will be identical to the co-primary MACE model results, with the following exceptions: The one-sided p-value presented will be for the test of superiority of daprodustat vs. rhEPO. The forest plot figure will not be created for the time to stopping study medication due to meeting rescue criteria endpoint. 	Model Results Presentation
 the number of occurrences (events), the number and percentage of subjects unable to be evaluated for rescue, and the number and percentage of subjects meeting rescue. The analysis model results presentation will be identical to the co-primary MACE model results, with the following exceptions: The one-sided p-value presented will be for the test of superiority of daprodustat vs. rhEPO. The forest plot figure will not be created for the time to stopping study medication due to meeting rescue criteria endpoint. 	
 the number and percentage of subjects meeting rescue. The analysis model results presentation will be identical to the co-primary MACE model results, with the following exceptions: The one-sided p-value presented will be for the test of superiority of daprodustat vs. rhEPO. The forest plot figure will not be created for the time to stopping study medication due to meeting rescue criteria endpoint. 	the number of occurrences (events),
 The analysis model results presentation will be identical to the co-primary MACE model results, with the following exceptions: The one-sided p-value presented will be for the test of superiority of daprodustat vs. rhEPO. The forest plot figure will not be created for the time to stopping study medication due to meeting rescue criteria endpoint. 	
 The one-sided p-value presented will be for the test of superiority of daprodustat vs. rhEPO. The forest plot figure will not be created for the time to stopping study medication due to meeting rescue criteria endpoint. 	• The analysis model results presentation will be identical to the co-primary MACE model results,
 vs. rhEPO. The forest plot figure will not be created for the time to stopping study medication due to meeting rescue criteria endpoint. 	
due to meeting rescue criteria endpoint.	
	Model Results Interpretation

• One-sided p-values will be compared to 0.025 to assess nominal significance.

Supportive Statistical Analyses

Subgroup Analysis

• Subgroup analyses will be performed for the time to rescue endpoint using the hyporesponder subgroup only (described in Section 10.10), in a method similar to that described for the subgroup analyses of the co-primary MACE analysis.

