10.10.2. Randomization Stratification

Randomization is stratified by dialysis type (HD or PD), region and by participation in an ABPM sub-study to ensure balance across treatment groups for both the overall parent study and within the ABPM sub-study. The prognostic stratification factors (i.e., dialysis type and region) will be taken into account within the analysis models. Stratification by ABPM sub-study participation was implemented for logistical reasons, and will not be taken into account within analysis models.

Baseline dialysis type strata will be identified by two data sources:

- PPD's IRT dataset
- eCRF

The proposed approach is to use the IRT strata in the adjusted analysis models in order to provide a randomization-based test statistic in accordance with the principle of 'analyze as randomized'. In summaries of subgroups however, the actual status of the factor for stratification derived from the eCRF form will be used. Additionally, subjects who change dialysis modality during the study will remain in the dialysis modality strata that was assigned at randomization.

200807

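### For two secondary hemoglobin endpoints the p-values are stratified but the intervals beside them are written without strata; stratifying the intervals would cost almost nothing.

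*SAP*

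**What the plan says.** All of this stands in SAP Section 8.1.2.2, Hgb Variability, unless another section is named.

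**% time in range.** "A van Elteren test (stratified Wilcoxon rank sum test) will be used to compare the percentage of time in range between treatment arms", adjusted for the prognostic stratification factors. A Mann-Whitney estimate with a 95% CI is also presented and is explicitly called stratified. The non-inferiority analysis "will use a margin of 15 percentage points less time in range". For that analysis the plan states: "Hodges-Lehmann estimate of the treatment difference will be used to assess non-inferiority in % time in range". Support for non-inferiority is claimed "if the lower limit of the two-sided 95% CI of Hodges-Lehmann estimate is above -0.15". The Hodges-Lehmann estimate is not called stratified, and no method is given for its interval. Superiority is assessed by the one-sided p-value only once non-inferiority is met.

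**Responders.** The test is CMH over the as-randomized prognostic factors. The display is the "difference in response rate (daprodustat vs rhEPO) and two-sided 95% CI using Wald method". A CMH-adjusted difference decides whether the one-sided p-value is p/2 or 1-p/2, but that adjusted difference is not listed for reporting. The interpretation rule is: "For the responder analysis, the one-sided CMH p-value will be compared to 0.025 to assess nominal significance".

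**Strata.** The synopsis (Section 1) describes dialysis type and region as potentially prognostic. Section 10.10.2 says: "The prognostic stratification factors (i.e., dialysis type and region) will be taken into account within the analysis models".

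**Status.** Section 2.2 lists both endpoints as secondary without multiplicity adjustment.

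**The concern.** When randomization is stratified and the strata predict outcome, an interval that ignores them counts between-stratum variation as noise. A stratified test removes that variation. Interval and p-value then answer slightly different questions.

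There are two consequences. A reader may see a significant CMH result beside a responder interval that includes 0. And the gated sequence for % time in range takes its first step on what reads as an unstratified comparison and its second step on a stratified one.

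The responder display has a further oddity. One difference (CMH-adjusted) signs the p-value, while another (unadjusted) is reported.

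**Working it through.** The SAP gives no sample size, SD, response rate, stratum sizes or prognostic strength for these endpoints, so there is no stated figure to reproduce. A one-sided 0.025 test and a two-sided 95% CI share the critical value 1.960, so any disagreement does not come from the error level.

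**Inputs from the SAP:** 1:1 allocation; dialysis type (2) by region (5), giving 10 cells; margin -15 points.

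**Assumed inputs:** R², the share of outcome variance explained by the strata, 0-10%; 500-1,500 per arm; SD 25-35 points; responder base rate 65%.

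**1. Width ratio.** Unstratified/stratified = 1/√(1 - R²).

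| R² | Ratio |
|---|---|
| 0 | 1.000 |
| 2% | 1/√0.98 = 1.010 |
| 5% | 1/√0.95 = 1.026 |
| 10% | 1/√0.90 = 1.054 |

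**2. In points of time in range.** As an approximation, half-width = 1.96 × SD × √(2/n per arm).

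- Widest case (SD 35, n = 500): 1.96 × 35 × 0.0632 = 4.34. Ignoring strata adds 4.34 × 0.026 = 0.11 at R² = 5%, and 4.34 × 0.054 = 0.24 at 10%.
- Narrowest case (SD 25, n = 1,500): 1.96 × 25 × 0.0365 = 1.79. Ignoring strata adds 0.05 and 0.10.

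The excess is therefore 0.05-0.24 points against a 15-point margin.

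**3. Responder simulation** (1,200 per arm, allocation balanced within 10 strata, true difference 5 points).

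| R² | Wald/stratified width | Wald and CMH conclusions differ |
|---|---|---|
| 0 | 1.00 | 0.1% |
| 2% | 1.01 | 0.6% |
| 5% | 1.03 | 1.5% |
| 10% | 1.06 | 3.5% |

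From R² = 2% upward every disagreement is CMH significant with the Wald interval including 0. With no true difference, disagreement was at most 0.4%.

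**4. % time in range simulation** (600 per arm, SD 30 before truncation to 0-100, 200 runs per setting). An unstratified Hodges-Lehmann interval is compared with one obtained by inverting van Elteren.

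| R² | Width ratio, true difference 0 / +3 / -12.5 | Meets the -15 margin at -12.5: unstratified vs stratified |
|---|---|---|
| 0 | 0.99 / 1.00 / 1.00 | 0.50 vs 0.52 |
| 5% | 1.05 / 1.04 / 1.03 | 0.45 vs 0.50 |
| 10% | 1.11 / 1.09 / 1.06 | 0.475 vs 0.55 |

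At true differences of 0 and +3 points both versions met the margin in 100% of runs at every R². The largest gap in half-width was (5.88 - 5.32)/2 = 0.28 points, at R² = 10% and no true difference. With 200 runs, a pass rate near 0.5 has a Monte Carlo SE of √(0.25/200) = 0.035, so the last column is only indicative.

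**5. Is disagreement on superiority for % time in range due to the strata?** At +3 points the Hodges-Lehmann interval and the van Elteren test disagreed in 13%, 9.5% and 16% of runs at R² = 0, 5% and 10%. It is already 13% when the strata explain nothing, so much of it comes from elsewhere, chiefly ties at 100%.

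**The case against.** The case for leaving the text alone has real weight.

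- **The SAP does not say that the Hodges-Lehmann interval ignores strata.** This stands. It is silent, and unstratified is an inference from the contrast with the labelled Mann-Whitney estimate.
- **Excess width needs prognostic strata, and the SAP gives no figure.** This stands. The synopsis says only that the factors are potentially prognostic.
- **Any error is conservative and small.** This stands: a wider interval cannot create false support for non-inferiority.
- **The Wald interval decides nothing.** This stands. The responder conclusion rests on CMH, and Section 7.2.2 similarly sets a Wald interval for a rate difference beside an adjusted Cox model. It remains the only interval a reader sees for that endpoint.
- **A stratified Mann-Whitney interval already accompanies van Elteren.** This is true, but the -0.15 criterion is tied to the Hodges-Lehmann interval.

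Three stronger readings are tempting, and the documents do not support them.

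- A reader might infer that the non-inferiority conclusion can contradict a test. It cannot: no non-inferiority p-value is planned for % time in range, and responders have no non-inferiority assessment.
- A reader might infer a breach of Section 10.10.2. That section speaks of analysis models, and a Hodges-Lehmann estimate or a simple risk difference is not one.
- A reader might infer serious over-coverage. Width excesses of a few percent do not imply it.

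**Conclusion.** The point holds as a minor, low-cost improvement. For two nominal secondary endpoints the tests are stratified, the responder interval is written without strata, and the construction of the Hodges-Lehmann interval is unstated.

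At an assumed R² of 5-10% the intervals would be about 3-5% (Wald) and 3-11% (Hodges-Lehmann) wider than stratified ones. The responder interval and CMH would disagree in about 1.5-3.5% of trials when the true difference is 5 points. At R² = 0 neither interval is wider.

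The effect on non-inferiority is a fraction of a point against 15, so the conclusion is unlikely to move unless the true difference is near the margin. Sample size, SD, response rate, stratum sizes and R² are all assumptions. The co-primary analyses and the Holm family of four principal secondary analyses (Section 10.11.1.2) are not touched.

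**What to change.** Amend Section 8.1.2.2 before unblinding.

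1. **Responders:** in place of the unadjusted Wald interval, report the Mantel-Haenszel weighted risk difference over the as-randomized dialysis type by region strata, with its stratified 95% CI. Use the sign of that same difference for the one-sided CMH p-value, so that one difference serves both purposes.
2. **% time in range:** specify the Hodges-Lehmann estimate and 95% CI for the -0.15 comparison as stratified by the same factors, obtained by inverting the van Elteren test. An interval built this way agrees with the superiority p-value by construction, including where ties would otherwise separate them.

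The cost is a few sentences and minor programming, with no new data. Some of the 10 cells may be small; the text should say how a cell with subjects from only one arm is handled, since it contributes nothing to either comparison.
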